The Effect of Pudendal Nerve Block Analgesia on Postoperative Pain Control in Patients Undergoing Vaginal Surgery: A Randomized Double-blind Placebo-controlled Trial

NCT04198714

Document date: 1/5/2021

 Protocol Title: Pudendal nerve block analgesia at the time of vaginal surgery: a randomized, double-blinded, placebo controlled trial

Short Title: PACE-72

2. Principal Investigator: [name]

Research Team:

[name] - Co-investigator and Study Coordinator

[name] - Co-investigator

[name] - Co-investigator

[name] - Co-investigator

[name] - Co-investigator

3. **Hypothesis/Specific Aims**: The objective of this this randomized controlled study is to determine whether a pudendal nerve block at the time of vaginal surgery is associated with improved postoperative pain control and decrease opioid consumption compared to a sham pudendal nerve block in patients undergoing vaginal surgery.

4. Primary, Secondary and Exploratory Endpoints:

Primary Endpoints:

[figure not shown]
- 1. Compare visual analog pain scores (VAS) the morning after vaginal surgery in women who received a pudendal nerve block or placebo / sham block.
- 2. Evaluate opioid analgesia given in the Post Anesthesia Care Unit (PACU) after vaginal surgery after receiving a pudendal nerve block intraoperatively.
- 3. Evaluate total opioid analgesia use in the first 24 hours after vaginal surgery after receiving a pudendal nerve block intraoperatively.

Secondary Endpoints:

- Compare patient satisfaction scores with postoperative pain control between women who received a pudendal nerve block or placebo / sham block during vaginal surgery
- Compare rates of postoperative urinary retention and other adverse events between women who received a pudendal nerve block or placebo / sham block during vaginal surgery.

5. Background/Significance:

Female pelvic floor disorders encompass multiple disorders of the genital and lower urinary tract and pelvic floor musculature, including pelvic organ prolapse, urinary and fecal incontinence, and pelvic pain syndromes. This family of disorders is estimated to affect up to 25% of all adult women in the United States with increasing prevalence with age.^{1,2} Surgical

treatment is often elected, with 1 in 5 women undergoing surgery for pelvic organ prolapse and/or incontinence by 80 years of age.³ Furthermore, the demand for such surgical interventions is estimated to increase up to 40% in the next 30 years, as the population ages in the United States.^{4,5}

6. Premise: Given the high prevalence of surgical management for pelvic floor disorders and the now recognized opioid crisis, it is imperative to optimize postoperative pain control in these patients. Historically, postoperative pain control has been largely focused on opioid medications, and very few studies have targeted vaginal surgery, which is central to surgical management of most pelvic floor disorders. A recent review identified only one study that evaluated postoperative pain control after vaginal reconstructive surgery, and the mainstay of therapy was opioid driven.^{6,7} The problematic use of opioid analgesia is now well documented, including side effects of nausea, vomiting, constipation, urinary retention, and central nervous system alterations, as well as the widely publicized addictive nature of the medications.^{6,8,9}

In order to minimize opioid use postoperatively, it is prudent to optimize multimodal therapy with non-narcotic analgesia. Use of treatments such as ice packs, NSAIDs and acetaminophen are effective, but we may also maximize analgesia with regional nerve blocks. ¹⁰ This may be particularly helpful for patients with contraindications to non-narcotic medications.

The objective of this this randomized controlled study is to determine whether a pudendal nerve block at the time of vaginal surgery is associated with improved postoperative pain control and decrease opioid consumption compared to a sham pudendal nerve block in patients undergoing vaginal surgery.

7. **Preliminary data**: In abdominal surgery, a transversus abdominis plane (TAP) block has been shown to improve postoperative pain control and reduce opioid consumption. During vaginal surgery, then, regional analgesia with a pudendal nerve block would be appropriate.

The pudendal nerve innervates much of the lower pelvis, including the pelvic floor musculature, the perineum and the urethral and anal sphincters. ^{13,14} Pudendal nerve blocks provide effective pain relief for patients with chronic pelvic pain and during childbirth. ^{15,16,17} In the acute perioperative setting, anesthesiologists have utilized preoperative pudendal blocks as an alternative to general anesthesia with improved subjective pain scores and decreased use of all postoperative pain medications. ^{18,19} Female pelvic surgeons demonstrated a reduction in NSAID use after sacrospinous ligament colpopexy with an intraoperative pudendal block. ²⁰

8. Feasibility (subject recruitment/anticipated problems/alternatives): We performed a power calculation and determined that we will need 30 patients in each arm in order to achieve a

90% power to detect a mean difference of $^{\sim}20$ mm on a 100mm VAS scale for a significance level of 0.05. We added 20% to this number to account for loss of follow up. In total, then, we will need **72** patients, **36** in each arm.

9. Approach / Specific Methodologies:

IRB approval will be obtained at MetroHealth Medical Center. This will be a randomized controlled trial that will be conducted at MetroHealth Medical Center. Preoperative written informed consents explicitly explaining the risks and benefits of the study will be obtained from the patients.

The inclusion criteria are the following:

- 1. Subject is willing to provide written informed consent
- 2. English speaking female ≥18 and ≤80 years of age
- 3. Subject is willing and able to comply with follow-up regimen
- 4. Subject is able to read a visual analog scale
- 5. Specific vaginal procedures include, but are not limited to:
 - Perineoplasty
 - Complete vaginectomy
 - Le Forte colpocleisis
 - Anterior repair, posterior repair, and/or enterocele repair
 - · Transvaginal mesh use
 - Transvaginal mesh excision
 - Sacrospinous ligament fixation
 - Uterosacral ligament suspension
 - Vaginal paravaginal defect repair
 - Midurethral sling placement
 - Pelvic floor injections
 - Sphincteroplasty
 - Vaginal hysterectomy, with or without removal of tube(s) and/or ovary(s), with or without repair of enterocele

The **exclusion** criteria are the following:

- 1. History of chronic pelvic pain
- 2. Currently taking sedatives
- 3. Liver disease
- 4. Renal disease
- 5. Intraoperative concern for increased blood loss
- 6. Unable to understand visual analog scales
- 7. Undergoing concomitant abdominal or laparoscopic procedures
- 8. Allergy to bupivacaine or triamcinolone
- 9. Patients who are ineligible for non-narcotic pain medications, such as acetaminophen and NSAIDs
- 10. Women who did not consent for the study
- 11. Unable to speak English
- 12. Unable to understand visual analog scales

Demographic factors are recorded including, age, BMI, ethnicity, preoperative diagnosis, comorbid conditions, and surgery performed. Intraoperatively, duration of anesthesia, duration of surgery, estimated blood loss and intraoperative medications are recorded for each type of surgery.

Once patients are selected and informed consents are obtained, they are randomized into the active and control groups using computer generated randomization with sequentially numbered opaque sealed envelopes.

The operating room nurse will randomly pick an envelope; half of them will indicate placebo and half will indicate medication. The nurse will then obtain the medication or saline as indicated. The attending physician will create the block. The fellow will then give the block or sham block. Only the attending physician ([name] or [name]) will be unblinded, and they will not do any block administration, data collection or analysis. Double blinding will be achieved by blinding of the patient and the practitioners that will administer the block, collect data, and perform data analysis. The surgical fellows, who will administer the block and perform the analysis, will be blinded to the medication. Only the attending surgeon ([name] or [name]) will be unblinded, and they will not do any block administration, data collection or analysis.

Depending on randomization, the patient will be given either an active or sham pudendal nerve block at the conclusion of surgery but while still under anesthesia. The ischial spine is palpated transvaginally. The medication is then injected through the vaginal tissues in the area of the ischial spine, which is where the pudendal nerve runs. Light pressure is then applied for a short period of time. This procedure is repeated on the contralateral side.

Pudendal Nerve Block:

9cc of 0.25% Marcaine + 1cc of 40mg/mL triamcinolone 5cc will be injected in the area of the pudendal nerve on each side.

Sham Block:

10cc normal saline

5cc will be injected in the area of the pudendal nerve on each side.

Once out of PACU, all patients will be ordered the same post-operative pain regimen, unless the patient has specific contraindications. These medications will be ordered through our standard postoperative order set. The medicine will be provided by the nursing staff as per pharmacy orders:

- 1. Acetaminophen PO 975mg q8h
- 2. Ketorolac 15mg IV Q6H x24 hours
- 3. Ibuprofen 600mg PO Q4H PRN for mild (1-3) pain after 24 hours
- 4. Oxycodone 5mg PO Q4H PRN for moderate (4-6) pain
- 5. Oxycodone 10mg PO Q4H PRN for severe (7-10) pain
- 6. Hydromorphone 0.2mg IV Q3H PRN for breakthrough pain
- 7. Patients will be discharged home with an appropriate pain regimen for the nature of their surgery acetaminophen and ibuprofen, with or without tramadol or oxycodone

- 10. Safety Plan: To ensure subject safety, [name], not otherwise engaged in the study, has agreed to monitor the study from the standpoint of subject safety. [name] will review the aggregate safety data and evaluate any safety issues that may arise during the conduct of study. The DSMB will review any individual adverse events. All adverse events will be documented. All reported adverse events will be graded using the Common Grading Scale:
 - 0 No adverse event or within normal limits or not clinical significant
 - 1 Mild AE, did not require treatment
 - 2 Moderate AE, resolved with treatment
 - 3 Severe AE, resulted in inability to carry on normal activities and required professional medical attention
 - 4 Life threatening or disabling AE
 - 5 Fatal AE

If [name] determines there is sufficient concern for subject safety, the IRB will be notified, and appropriate actions will be taken. Adverse events will be followed until closure or documented as chronic. Safety Monitoring will also be established in the statistical analysis.

Data and safety monitoring will be performed by the study team and [name] throughout the study to ensure all policies are being followed. Study investigators will actively monitor for unanticipated problems, adverse events, or protocol deviations, with specific emphasis on any events involving risk to subject or others. The patients will be monitored closely in the hospital for any abnormalities which is standard for perioperative care. Investigators will again address any questions or concerns during the scheduled postoperative telephone follow up to discuss the questionnaire. Any unexpected or significant adverse event may prompt a preliminary statistical analysis and/or immediate halt in enrollment or cancellation of the study.

Record of any adverse events will be kept in a Safety Monitoring Log. Monitoring will take place during preoperative communication with patient, during hospital stay, at the follow-up phone call, and in the postoperative period. In addition to monitoring and record keeping, events will be reported as appropriate. Unanticipated problems and any adverse events that may change the risk/benefit ratio will be reported to the IRB within 3 days of discovery per institutional guidelines. Serious adverse events will be immediately reported to the IRB and the patient's primary provider as soon as the investigator is aware of the incident. Any adverse events that are felt to alter the risk/benefit ratio of the study may prompt a review and revision of study protocol and/or consent form.

Any internal Serious Adverse Events related to the study will be reported to the IRB within 24 hours of site awareness per IRB Reporting Guidelines.

- 11. Statistical Analysis: Data will be kept in RedCap. Statistical analysis will be performed using statistical software, GraphPad or STATA. Continuous variables will be analyzed using the t-test/Mann-Whitney test, and categorical variables will be analyzed using Chi-Square methods.
- 12. **Budget**: The patient's insurance will be charged for the block. We use local anesthetic routinely in pelvic surgery, with virtually every case, so these medications will be provided as part of standard perioperative care. We are not aware of cases of insurance not covering these medications or standard local anesthesia.

Any additional necessary budget will be internal from residual funds.

- 13. Study Time Lines: We expect recruitment to take approximately one year.
- 14. Appendix (study visit grid): N/A

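### Three unranked primary endpoints and no rule for success: the stated 0.05 and 90% describe the VAS test, not the trial's primary decision

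*Combined protocol and SAP*

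**What the plan says.** Section 4 puts three numbered items under a plural primary heading, with a separate secondary list below. The first concerns pain and names both arms: "Compare visual analog pain scores (VAS) the morning after vaginal surgery in women who received a pudendal nerve block or placebo / sham block". The second turns to the recovery unit and names no comparator: "Evaluate opioid analgesia given in the Post Anesthesia Care Unit (PACU) after vaginal surgery after receiving a pudendal nerve block intraoperatively". The third widens the window to a full day, again without a comparator: "Evaluate total opioid analgesia use in the first 24 hours after vaginal surgery after receiving a pudendal nerve block intraoperatively".

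None is ranked or singled out. The aim in Section 3, repeated in Section 6, is to learn whether the block "is associated with improved postoperative pain control and decrease opioid consumption compared to a sham pudendal nerve block in patients undergoing vaginal surgery".

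Section 8 has the only power calculation. It asks for 30 per arm, sets power at 90%, and targets a gap of about 20 "mm on a 100mm VAS scale for a significance level of 0.05". Sidedness and SD are not stated. On attrition the section says "We added 20% to this number to account for loss of follow up", which gives 36 per arm and 72 in total.

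Section 11 assigns the t-test or Mann-Whitney test to continuous variables and chi-square methods to categorical ones. It gives no testing order, alpha split, adjustment or definition of a positive trial.

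**The concern.** A reader cannot tell whether one particular endpoint, any endpoint or all three must succeed. Followed literally, the plan produces three unadjusted primary tests. A primary claim could rest on whichever falls below 0.05, or the success rule could be settled once results are known. The significance level and power in Section 8 belong to one of the three tests. Unless that test alone decides the trial, they are not the trial's error rate or power.

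**Working it through.** **Inputs from the plan.** Three primary endpoints (Section 4); significance level 0.05, power 90%, difference about 20 mm, 30 per arm, 20% added (Section 8); two-group tests (Section 11).

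**Assumptions.** Two-sided testing, the correlations between endpoints, the VAS SD and the power of the opioid tests. None of these is in the plan.

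**The plan's own figure.** 30 × 1.2 = 36 per arm and 2 × 36 = 72, so the add-on reproduces. The 30 cannot be checked independently because no SD is given. Solving backwards for a two-sided t-test with 30 per arm and 90% power gives a standardised difference of 0.851, so SD = 20 / 0.851 = 23.5 mm. With that SD, VAS power is 90% at 30 evaluable per arm and 94.5% at 36.

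**Reading A: VAS alone decides.** Error 5%, power as stated. Nothing breaks.

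**Reading B: any one of three suffices, each at two-sided 0.05.** If the tests are independent and all nulls are true, the error is 1 − 0.95³ = 0.143. With correlated normal statistics, the probability that at least one |z| exceeds 1.96 is:

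| Correlation | Familywise error |
|---|---|
| common 0.3 | 13.6% |
| common 0.5 | 12.5% |
| common 0.7 | 10.9% |
| common 0.8 | 9.8% |
| common 0.95 | 7.3% |
| VAS-opioid 0.3, opioid-opioid 0.5 | 13.2% |
| VAS-opioid 0.3, opioid-opioid 0.8 | 12.1% |
| VAS-opioid 0.5, opioid-opioid 0.8 | 11.5% |

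The mixed rows matter because the two opioid measures may be closely related. The plan does not say whether the 24-hour total includes PACU doses.

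**Reading C: all three must succeed.** Type I error is at most 5%. Power cannot exceed that of the weakest test, so it cannot exceed VAS power: 90% at 30 evaluable per arm, about 94.5% at 36. The actual value is unknown without opioid effect sizes and SDs. For illustration, give each opioid test 90% power:

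- At 30 per arm: 0.90 × 0.90 × 0.90 = 73% if independent, rising to 83% at common correlation 0.8.
- At 36 per arm: 0.945 × 0.90 × 0.90 = 77% if independent, rising to 85% at 0.8.

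**Comparing two remedies.** Suppose there is no VAS effect and each opioid test has 80% power at 0.05. Correlations range from 0 (VAS-opioid) with 0.5 (opioid-opioid) to 0.5 with 0.9.

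- A fixed sequence starting with VAS, opened only by a VAS result favouring the block, yields a 24-hour opioid claim in about 2.0-2.5% of trials.
- Holm across all three yields it in about 68-69%.

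Holm's cost falls on VAS. Holm always rejects VAS when p ≤ 0.05/3, so power at that level is a lower bound. With SD 23.5 mm and a t-test it is 79% at 30 and 87% at 36 evaluable per arm. With Mann-Whitney on normal data it is about 76% and 85%.

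**The case against.** The strongest reply is that VAS is the primary endpoint in all but name. It is listed first, it alone is powered, and items 2 and 3 speak of evaluating opioid use without naming a comparator. This reading is available, and under it the stated figures hold. But the text does not adopt it: all three items carry the primary label although a secondary list follows directly, and the aim, given twice, sets opioid consumption against sham alongside pain control.

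A second reply is that the aim joins pain control and opioid use with *and*, which suggests that both must be shown, and a joint requirement does not inflate type I error. That also stands as a possible reading. The difficulty then moves to power, which the plan addresses for only one of the three tests.

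It follows that a reader might infer too much in two ways. One is that the plan runs at an 11-14% error rate; no section says that any one endpoint suffices, so that figure is conditional. The other is that 90% caps the power of a joint rule; the 90% refers to 30 evaluable per arm, and 36 are to be enrolled.

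A third reply is that Holm could be added later without harm because it needs no ranking. It does not hold: choosing Holm over VAS-only after seeing results is itself data-dependent. A VAS p-value of 0.03 with null opioid results succeeds under VAS-only and fails under Holm.

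A figure under the primary heading was not visible to me. No text elsewhere refers to a ranking or an adjustment.

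**Conclusion.** The concern holds as an unspecified primary decision rule. The plan's 0.05 and 90% describe the VAS test and carry over to the trial only if VAS alone decides, which the plan does not say. If any one endpoint suffices, the 5% level is lost across the whole range examined: about 11-14% at low to moderate correlations, about 10% at a common 0.8 and about 7% at 0.95. If all three are required, the level is held but power is unknown and cannot exceed that of VAS.

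That the rule is missing rests on the text alone. The sizes rest on assumed two-sided tests, correlations and opioid powers, and on an SD inferred from the plan's own power claim. The gap governs the trial's main conclusion and can be closed credibly only before results by arm are seen, so it should be corrected before unblinding.

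**What to change.** **Preferred, before unblinding.** In Section 4, name next-morning VAS as the single primary endpoint, tested at two-sided 0.05. Make 24-hour opioid use and then PACU opioid use key secondary comparisons with sham. In Section 11, state that they are tested in that fixed order, each only if the previous result is significant in favour of the block, and are otherwise reported with confidence intervals. The 24-hour measure comes first because it is the broader reflection of the aim; the sponsor may reverse the order if this is fixed in advance.

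*Cost.* Re-labelling and one or two sentences. The 72 patients and the power statement stay. The real loss is that an opioid benefit without a VAS benefit could not be claimed as confirmatory (the 2.0-2.5% above). This is not remote: under Section 9, as-needed oxycodone after PACU is tied to the pain score, so benefit could show as less opioid at similar VAS. That argument does not extend to the PACU endpoint, since the regimen starts after PACU.

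**Alternative, if the sponsor wants an opioid result to count by itself.** Keep all three as primary, each written as a comparison with sham, and specify Holm, also before unblinding. Restate VAS power as at least about 79% at 30 and 87% at 36 evaluable per arm (t-test, assumed SD 23.5 mm), and give the SD on which it rests. The choice depends on what the sponsor intends to claim.

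### Does adding 20% to 30 per arm leave the trial short of patients if 20% are lost?

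*Combined protocol and SAP*

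**What the plan says.** Section 8 (Feasibility) holds the whole sample-size argument. It opens with "We performed a power calculation and determined that we will need 30 patients in each arm in order to achieve a" and continues "90% power to detect a mean difference of" about 20 mm on a 100 mm visual analogue scale (VAS), at a significance level of 0.05. It then says "We added 20% to this number to account for loss of follow up" and concludes "In total, then, we will need 72 patients, 36 in each arm".

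The section gives no standard deviation, does not say whether the test is one- or two-sided, and states no expected loss rate apart from the 20% added. Section 4 lists the VAS comparison as the first primary endpoint: "Compare visual analog pain scores (VAS) the morning after vaginal surgery". Section 11 says how such outcomes are tested: "Continuous variables will be analyzed using the t-test/Mann-Whitney test".

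**The concern.** Two operations are easily confused. Adding 20% to the evaluable number multiplies it by 1.20. Protecting that number against 20% loss means dividing it by 0.80. The second gives the larger answer, because the loss is a share of those enrolled and not of those who remain. Loss to follow-up is the only purpose given for the 20%, so a reader will naturally take it as the loss the trial can bear. On that reading the plan enrols too few: after 20% loss fewer than 30 per arm would be evaluable, and the 90% power would not quite hold. A published sample-size paragraph that repeated the wording could then suggest a tolerance that 72 patients do not provide.

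**Working it through.** **Inputs.** From Section 8: 30 evaluable per arm, 90% power, a difference of about 20 mm, significance level 0.05, 20% added, 36 per arm, 72 in total. Assumed, because it is not stated: a two-sided test. Back-solved, because it is not stated: the standard deviation (SD).

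**1. The plan's own figure.** 30 × 1.20 = 36 per arm, and 2 × 36 = 72. This matches Section 8 exactly.

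**2. The loss that 36 per arm can absorb.** 1 − 30/36 = 6/36 = 16.7%.

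**3. What 20% loss would leave.** 36 × 0.80 = 28.8 per arm, or 57.6 of 72. In whole patients that is 28 or 29 per arm.

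**4. Enrolment that keeps 30 at 20% loss.** 30/0.80 = 37.5, so 38 per arm and 76 in total (75 if rounded on the total, 60/0.80).

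**5. Implied SD.** For a two-sample t-test with n per arm, the noncentrality is λ = 20 / (SD × √(2/n)) on 2n − 2 degrees of freedom, and power is the probability that a noncentral t variable exceeds the two-sided 5% critical value. Setting n = 30 and power 90% gives SD = 23.5 mm, with λ = 20 / (23.5 × 0.2582) = 3.30. The normal approximation gives 23.9 mm.

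**6. Power with that SD and a true difference of 20 mm.**

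| Evaluable per arm | Power, two-sided t-test |
|---|---|
| 36 (no loss) | 94.5% |
| 30 (16.7% loss) | 90.0% |
| 29 | 89.0% |
| 28.8 (20% loss) | 88.8% |
| 28 and 29 | 88.4% |
| 28 | 87.9% |

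At 20% loss the shortfall is 90.0 − 88.8 = 1.2 points, or 90.0 − 88.4 = 1.6 points with 28 in one arm and 29 in the other. If the test were one-sided, the implied SD would be 26.2 mm and power at 28.8 per arm 88.9%, so sidedness hardly matters here.

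**7. Can so small a gap be resolved from what is stated?**
- Sample sizes are rounded up, so 30 per arm does not pin the SD to a single value. With the t-test, any SD from about 23.1 to 23.5 mm rounds up to 30. At 23.1 mm the same formula gives 89.8% at 28.8 per arm, a shortfall of 0.2 points.
- The target difference is approximate. With the SD at 23.5 mm, 28.8 per arm gives 90% power for about 20 × √(30/28.8) = 20.4 mm, which still fits a target of about 20 mm.

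**The case for a change.** The strongest case for a change is that the 20% is tied explicitly to loss, so the section at best leaves the tolerated loss unclear, and one sentence would settle it at no cost in patients. That is fair as a remark on reporting. It does not show a wrong figure: the protocol says what was done to the 30, and the result is right for that operation. The 20% loss rate is the reader's inference.

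A second argument is that the six spare patients per arm might also have to cover exclusions during surgery, since Section 9 excludes patients for intraoperative concern about blood loss and describes randomization once consent is obtained. The same section has the operating room nurse draw the envelope and the block given at the end of the operation. It does not say whether the exclusion is applied before or after the draw. If before, no randomized place need be lost. The point remains open and cannot be counted as a shortfall.

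A third argument is that without the SD the 30 per arm cannot be checked independently. This is true, and it matters more than the inflation step: at 30 per arm, power would be about 97% with an SD of 20 mm and 72% with 30 mm (an assumed range). But it concerns the base number and says nothing about whether 20% was added correctly. The sponsor reports having done the calculation, so it should be able to supply the SD on request.

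On the other side, 20% loss may well be pessimistic for the VAS endpoint. It is measured the morning after surgery, and Sections 5 and 6 of the protocol are not needed to see that this is soon after the operation; Section 9 has nursing staff giving the analgesics and Section 10 describes monitoring in hospital. This too is an inference, because no loss rate is given.

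**Conclusion.** No change is needed. The inflation is correct as described, and 30 per arm is retained for any loss up to 16.7%. Only beyond that does the evaluable number fall below target. At 20% loss the deficit would be about one patient per arm, with power of roughly 88% to 89% against 90%, assuming a two-sided t-test, a difference of 20 mm and an SD near 23.5 mm. With the SD unstated and the difference given only approximately, a gap of one to two points cannot be told apart from rounding.

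Rewording Section 8 would leave 72 patients, the tests in Section 11 and the trial's conclusions as they are. The expected loss, SD and sidedness are missing details that the trial team can supply when the sample-size paragraph is written for publication.

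### Pre-operative opioid use and pain are not listed among the recorded baseline variables, and no analysis adjusts for them, although the primary endpoints are two opioid totals and a pain score

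*Combined protocol and SAP*

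**What the plan says.** Section 4 names three primary endpoints: "Compare visual analog pain scores (VAS) the morning after vaginal surgery", "Evaluate opioid analgesia given in the Post Anesthesia Care Unit (PACU) after vaginal surgery" and "Evaluate total opioid analgesia use in the first 24 hours after vaginal surgery".

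Section 9 gives the data to be collected. Before surgery: "Demographic factors are recorded including, age, BMI, ethnicity, preoperative diagnosis, comorbid conditions, and surgery performed". During surgery: "Intraoperatively, duration of anesthesia, duration of surgery, estimated blood loss and intraoperative medications are recorded for each type of surgery". Neither sentence mentions opioids taken before surgery or a pain score before surgery, and no other section does. The study visit grid in Section 14 is marked not applicable.

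The exclusion criteria in Section 9 include "Currently taking sedatives" and "History of chronic pelvic pain". No criterion names opioids. Inclusion criterion 4 reads "Subject is able to read a visual analog scale".

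Section 9 describes computer-generated 1:1 allocation by sealed envelope and states no stratification. Section 11 plans t-tests or Mann-Whitney tests for continuous variables and chi-square methods for categorical ones, with no covariates.

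**The concern.** Opioid use before surgery is an obvious candidate predictor of opioid use after it, and pain before surgery of pain after it. A patient who takes opioids for a condition other than chronic pelvic pain can enter the trial. If that is neither recorded nor used in the analysis, the variation it causes stays in the error term of the two opioid comparisons.

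With 36 patients per arm, a handful of users can also fall unevenly. A baseline table without the variable would not show this, and no sensitivity analysis could respond to it. A reader of the results would then be left to wonder how far a difference in opioid totals, or the lack of one, reflects who happened to be in each arm.

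**Working it through.** **1. The plan's own figure.** Section 8 states 30 per arm for 90% power to detect about 20 mm on a 100 mm VAS at a 0.05 level, and gives no SD. Taking the test as two-sided (the sidedness is not stated), the implied SD is 20 / [√(2/30) × (1.960 + 1.282)] = 20 / (0.2582 × 3.242) = 23.9 mm by the normal approximation, or 23.5 mm from the noncentral t. The standardized effect is 20 / 23.5 = 0.85. The enrolment step reproduces: 30 × 1.2 = 36 per arm, 72 in total.

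**2. Assumptions for the opioid endpoints.** The documents give no SD, effect size or power for them, and no prevalence of pre-operative opioid use. I therefore assume a standardized effect of 0.85, borrowed from the VAS. A proportion p of patients are opioid users, and their totals run k SD higher. The range is p = 5% to 15% and k = 1 to 3.

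**3. Extra variance left in an unadjusted comparison.** Variance is multiplied by 1 + p(1 − p)k²:

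- p = 0.05, k = 1: 1 + 0.05 × 0.95 × 1 = 1.05
- p = 0.10, k = 2: 1 + 0.10 × 0.90 × 4 = 1.36
- p = 0.15, k = 3: 1 + 0.15 × 0.85 × 9 = 2.15

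By the noncentral t at 30 per arm, a t-test that would otherwise have 90% power has 89%, 79% and 60% respectively.

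**4. Rank tests at 36 per arm.** This is by simulation, with normal outcomes within users and non-users. Ranges show the spread between separate runs.

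| Users, excess | Mann-Whitney | van Elteren, stratified by pre-operative use |
|---|---|---|
| 5%, 1 SD | about 93% | about 93% |
| 10%, 2 SD | 86–87% | about 93% |
| 15%, 3 SD | 74–76% | about 93% |

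With the block effect set to zero, both tests reject in about 5% of simulated trials in every row.

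**5. Chance imbalance.** With two independent Binomial(36, p) counts, the arms differ by 3 or more users with probability 17%, 32% and 41% at p = 5%, 10% and 15%.

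**6. Empty strata.** At p = 5% an arm has no users with probability 0.95^36 = 0.16, so at least one arm has none with probability 1 − (1 − 0.16)² = 0.29. A stratum present in only one arm adds nothing to a stratified test.

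**7. Pre-operative VAS.** Adjusting for a baseline score with outcome correlation r multiplies the SD by √(1 − r²). The correlation is an assumption. At 30 per arm and 20 mm:

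- r = 0.2: variance × 0.96, power 91.1%
- r = 0.3: variance × 0.91, power 92.5%
- r = 0.4: variance × 0.84, power 94.3%

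Against 90% unadjusted, the gain is about 1 to 4 points. A chance baseline imbalance shifts the VAS difference by up to 1.96 × r × 23.9 × √(2/30) mm (95% range), which is ±2.4 mm at r = 0.2 and ±4.8 mm at r = 0.4, against a 20 mm target.

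**The case against.** The strongest reply is that nothing here is wrong with the planned tests. Under randomization an unadjusted comparison already allows for chance imbalance, and adjustment is an efficiency gain. That stands. A reader might infer that uneven opioid use would bias the trial or inflate false positives. The documents do not support this, and the type I error in step 4 stays at its nominal level.

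Three other strong readings also fail:

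- **That the data will not be collected, or could never be recovered.** The Section 9 list is opened by the word *including*, so it need not be complete. Comorbid conditions might capture part of the information, and no case report form is shown. Screening for sedatives suggests that current medication is looked at, although no section describes a medication review. The supportable statement is that the items are not listed, so their collection is not assured.
- **That a baseline pain score already exists and only needs writing down.** Criterion 4 asks whether the patient can read a VAS. It does not say that a pain score is marked, so a pre-operative score would be a new measurement, though a brief one.
- **That the lower power figures are forecasts.** Prevalence, excess and effect size for the opioid endpoints are all assumed, and the 90% anchor belongs to the VAS. The exclusion of chronic pelvic pain plausibly removes some heavier users and narrows baseline pain, which points toward the smaller gains. The documents cannot settle this.

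What remains is that two primary endpoints are opioid amounts, opioid users may enter, and the plan neither lists nor uses the most direct baseline predictor.

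**Conclusion.** The point holds as a matter of precision and interpretability, not of bias or validity. For the opioid totals, stratifying gains nothing visible at 36 per arm if 5% of patients are users running 1 SD higher, about 6 to 7 points of power at 10% and 2 SD, and about 17 to 19 points at 15% and 3 SD. These figures assume the VAS standardized effect of 0.85 and normal outcomes within strata. Real opioid totals may be skewed, so they illustrate the direction and rough scale only. The VAS part is weaker, at 1 to 4 points for assumed correlations of 0.2 to 0.4, and is an optional refinement. The change is worth making because it is cheap and because an unlisted variable may not be available when an imbalance is suspected.

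**What to change.** 1. In Section 9, add pre-operative opioid use (none or any, and daily amount) to the recorded baseline variables.
2. In Section 11, prespecify that PACU and 24-hour opioid totals are compared with a rank test stratified by pre-operative opioid use (van Elteren), or with rank ANCOVA if a stratum is empty in one arm. Fix that rule in advance, and keep the unadjusted test as a sensitivity analysis. Recording without this step leaves power unchanged.
3. As a lesser item, record a pre-operative VAS pain score under stated conditions, and compare the morning-after VAS with a linear model on arm and that score.

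Eligibility stays as it is. The cost is one or two form fields, a brief extra measurement if item 3 is adopted, one or two degrees of freedom, and possibly a few missing baseline values. If opioid users turn out to be rare, the gain will be small.
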